6. INCLUSION AND EXCLUSION CRITERIA*

Aim 1 Study Population (20 adolescent e-cigarette users (Peer Advisory Panel) and two key informants)

The study population will be derived from 20 adolescent e-cigarette users in one high school selected for its high rate of racial/ethnic minorities and low SES status. We will also recruit two key informants (school nurse and Vice Principal) from the same high school.

Inclusion criteria for peer advisory panel: (1) enrolled in grade 9-12 at a local high school; (2) current e-cigarette user; (3) have a smartphone; and (4) English- or Spanish-speaking. Current e-cigarette user is defined as a response greater than “0 days” to the question: “During the past 90 days, on how many days did you use e-cigarettes?” This eligibility criterion is modeled on a question in the 2018 National Youth Tobacco Survey (NYTS), a survey of U.S. middle and high school students which used a 30-day timeframe.

Exclusion criteria for peer advisory panel: (1) unable or unwilling to provide informed assent or consent (in the case of those aged 18 years or older).

Inclusion criteria for two key informants: (1) employed as a school nurse or Vice Principal at the Aim 1 high school.

Exclusion criteria for two key informants: (1) unable or unwilling to participate in the study.

Aim 2 (80 adolescent e-cigarette users and up to 12 key informants)

In Year 2 of the project, 80 adolescent e-cigarette users in 4-7 high schools selected for their high rates of racial/ethnic minorities and low SES status (20/school, 40/study condition) will be recruited and complete assessments at baseline and 6-month follow-up.

Inclusion criteria for 80 adolescent e-cigarette users: (1) enrolled in grade 9-12 at a participating high school; (2) current e-cigarette user; (3) have a smartphone; and (4) English- or Spanish-speaking. Current e-cigarette use is defined as a response greater than “0 days” to the question: “During the past 90 days, on how many days did you use e-cigarettes?” This eligibility criterion is modeled on a question in the 2018 National Youth Tobacco Survey (NYTS), a survey of U.S. middle and high school students which used a 30-day timeframe.

Exclusion criteria for 80 adolescent e-cigarette users: (1) unable or unwilling to provide informed assent or consent (in the case of those aged 18 years or older).

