With participant permission, we will collect complete and accurate contact information from the student at baseline, including home address, phone, cell phone, email, and phone numbers of three contacts and best times and days to reach them to maximize retention. A contact sheet will be completed by the participant that will include the above information. Care will be taken to maintain the confidentiality of the student's participation; therefore all students will be asked to provide us with the individuals or contact information where they feel comfortable being contacted by study staff or where they feel assured that the confidentiality of their participation will be maintained. The other contacts provided by the student will not be informed of the student's vaping status. We have found in prior studies that cell phone numbers and e-mail addresses are particularly helpful in remaining in contact with this population. Tracking procedures will be implemented for any student who does not attend a scheduled study visit or who is not accessible by telephone or e-mail at the contact location provided. Attempts to locate students will be made mainly through the schools and by telephone calls to the contacts provided or directory assistance.

Table 2. Study Assessments, Measures and Data Collection Timing

Variable and Measure	Relevant Aim	Baseline	6-month follow-up
Recruitment: # screened and eligible, # and reasons for refusal	2A	•	
Retention: # of dropouts, reasons for dropping out	2A		•
Engagement (V2V only): # of completed responses to texting quizzes, peer videos viewed, peer coaching interactions	2B		*
Acceptability and satisfaction: Client Satisfaction Questionnaire (CSQ-8) semi-structured interview	2B		•
Cotinine-validated 7-day point prevalence abstinence: saliva samples collected from all; analyzed for those reporting 7-day abstinence; cut-off 11.4 ng/ml	2C		•
E-cigarette use frequency (past 7 and 30 day) and intensity (# days and amount vaped in past 7 and 30 day)	2C	•	•
THC/marijuana and other tobacco use frequency (past 7 and 30 day) and intensity (# days and amount vaped)		•	•
Social Cognitive Theory (SCT) constructs			
Self-efficacy, confidence to quit: Self-efficacy Questionnaire (SEQ-12)		•	•
Demographics and tobacco use			
Demographics: age, gender, socio-economic status, race/ethnicity, grade in school, academic performance		•	•
History of all tobacco use, past and recent quit attempts, cessation strategies used		•	

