Data collection: Data collected from participants will be obtained through interviews, paper and pencil surveys, and collection of saliva samples for cotinine assessment by the Research Coordinator in-person at the school nurse office at baseline and 6-months post-study entry. The student survey and assessment tools for this study will be adapted from our prior adolescent smoking cessation trials and will be submitted to the IRB for review and approval prior to use in the study. Survey and assessment tools are described in Table 2 on page 10 of the ISP. Data confidentiality will be emphasized on the surveys and verbally by the Research Coordinator (see section #30), and by the use of a unique identification number. Data will be entered into the regulated environment through a secure Research Electronic Data Capture (REDCap) form. REDCap is a secure web application for building and managing online surveys and databases that was funded by the National Institutes of Health. REDCap data is also stored in a regulated environment. These files will be deleted after study completion. Portable devices used to collect data (audio and film recordings) will be UMMS-issued devices and files will not be encrypted during the recording, but the recordings will be transferred as soon as possible (i.e.: typically within the same day) to UMMS servers. Once the files are transferred, they will be deleted from the portable devices.

We will conduct biochemical verification using a saliva NicAlert® test (Nymox Corporation), which is a semi-quantitative method that uses a dipstick to measure the level of cotinine in a sample of saliva. The test strip displays the result in seven zones with each zone representing a range of levels of cotinine/smoking (e.g.: zone 0 [0 – 10 ng/mL, a nonsmoker] to zone 6 [>1000 ng/mL, a heavy smoker]). The results are read as 0-6, and as recommended, any value ≥ 1 is considered as tobacco use. Research staff will enter these values into the database, using the participant ID as an identifier, and destroy the samples.

Data Analysis:

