Aim 2C (Cessation Outcomes) *Hypothesis H2: The intervention will be associated with greater cotinine-validated 7-day point prevalence vaping abstinence rates, lower time to first quit attempt, and less amount of e-cigarette use compared to control at 6-month follow-up.* We recognize that there is some controversy about estimating effect sizes from pilot studies. However, we are calculating effect sizes in our study to provide a range, recognizing that there might be uncertainties because of our small sample size. To estimate effect sizes for V2V intervention versus control, between-condition differences over time will be estimated for **cotinine-validated 7-day point prevalence abstinence** using GEE logistic regression with a random effect for school and fixed effects of condition, time point (baseline and 6 months), and their interaction. Missing data is handled using inverse probability weighting. By taking the repeated measurements into consideration, the GEE model is able to increase the power to test the difference in the outcome. COX regression modeling will be used to examine the intervention effect on **time to first quit attempt** adjusting for other covariates. **Amount of e-cigarette use** will be calculated as a reduction from baseline. We will model this reduction using negative binomial regression modeling if the variance of the distribution of risk reduction is over dispersed.

Other information important for the design of a future study includes standard deviations, as well as **preliminary assessment of possible mediators** such as engagement, behavioral capability, and self-efficacy. We will identify important mediators in exploratory analyses. Guided by the conceptual model based on SCT, we will assess effects of intervention on the mediator and the

effects of the mediator on the outcome, controlling for other mediators in the model, and confounders of the mediator-outcome relationship, and then estimate the proportion of the intervention effect explained. Given the limited sample size, conclusions from the mediation analyses will be limited and treated with caution, but modeling will allow us to explore the constructs of SCT and potential predictors towards a larger RCT.

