or older, and the video release form that there is no limit on the length of time we will store the peer videos and that it is possible that we might use the peer videos in future iterations of the V2V Intervention.

Data collected from participants will be obtained through interviews, paper and pencil surveys, writing sessions, and collection of saliva samples for cotinine assessment by the Research Coordinator, in-person at the school nurse office at baseline and 6-months post-study entry. Data confidentiality will be emphasized on the surveys and verbally by the Research Coordinator, and by the use of a unique identification number. Data will be entered into the UMMS regulated environment through a secure Research Electronic Data Capture (REDCap) form. Data (excluding peer videos) will not be distributed. Peer videos will be distributed to study participants via a secure website (example: Vimeo), and will be password protected. With the exception of the peer videos, we will retain study records and documents for a period of 3 years after the completion of the study.

See also #13, *Data Analysis and Management*.

Protection for Risks Associated with Potential Loss of Confidentiality

The study team have systems, oversight, experienced personnel, and an organizational culture that supports the appropriate use, access and storage of confidential information. All persons collecting or handling data will be trained in human subjects' procedures, confidentiality and privacy protection. All investigators and project staff are required to receive and complete Human Subjects and HIPAA training. All research personnel will hold a current Human Subjects Training Certificate.

Because the study will be funded by the NIH, we will follow the guidelines in the NIH certificate of confidentiality. The certificate keeps us from sharing identifiable sensitive information collected for the research unless the participants allow us to do so. This is included in the assent and consent form that was included as part of this IRB application. We will only disclose information about the students if they plan to harm themselves or others, or if they have a clinically significant score on the psychosocial factors scales included in the baseline and follow up data collection forms. We will not be disclosing information about illicit drugs issues to law enforcement agencies, parents, the school, or others.

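### For students whose cotinine stays in zone 0 while they vape, the strip cannot refute a false claim of abstinence, so their cotinine-validated result is self-report

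*Combined protocol and SAP*

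**What the plan says.** Section 6 defines a current user for Aim 2 by an answer above zero to "During the past 90 days, on how many days did you use e-cigarettes". Neither the nicotine content of the product nor a minimum frequency is a condition. The criteria exclude a student only on this ground: "Exclusion criteria for 80 adolescent e-cigarette users: (1) unable or unwilling to provide informed assent or consent".

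Hypothesis H2, repeated in Section 13 under Aim 2C, expects "greater cotinine-validated 7-day point prevalence vaping abstinence rates" in the intervention arm. The behaviour being validated is vaping, not nicotine intake.

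On the check itself, Section 13 says "We will conduct biochemical verification using a saliva NicAlert® test". Zone 0 covers 0 to 10 ng/mL, and "any value ≥ 1 is considered as tobacco use". No other biomarker is named. The Table 2 row in Section 11 reads "saliva samples collected from all; analyzed for those reporting 7-day abstinence; cut-off 11.4 ng/ml" and is marked at 6 months only. Sections 13 and 26 instead have saliva for cotinine taken "in-person at the school nurse office at baseline and 6-months post-study entry". Neither says what a baseline result would be used for. The abstinence model in Section 13 has condition, time and their interaction, with no term or restriction for baseline cotinine.

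**The concern.** A cotinine strip verifies vaping abstinence only in someone whose vaping would raise cotinine above zone 0. The entry rule does not secure that. It admits nicotine-free use and use so light or infrequent that the strip may not register it. For these students a reading of 0 at 6 months does not separate a quitter from a continuing vaper who says they have quit.

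At stake is what the label means. The plan wants the abstinence comparison as an effect-size range for a later trial. If an unknown part of that outcome is unverified self-report, the range carries a misclassification error that a larger sample under the same rule would repeat. The caution in Section 13 about pilot effect sizes concerns small numbers, not this error.

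**Working it through.** **The plan's own figure.** The only precision calculation concerns retention, and it reproduces: design effect 1 + 0.01 × (20 − 1) = 1.19; 40 / 1.19 = 33.6, rounded to 34; exact 95% interval for 29/34 = 68.9% to 95.0%. This point does not affect it.

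**Is the group plausible?** Section 5 says 28% of high-school users vape on 20 or more days a month, so 72% vape on fewer. The 90-day window is wider than the 30-day survey question it is modelled on, so it can admit lighter users still. Neither fact gives the share who would read zone 0.

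**Model.** Let p be true abstinence, m the share of continuing vapers who claim abstinence, and f the share of continuing vapers who would read zone 0. Assume the strip catches every other false claim. Then

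observed validated rate = p + (1 − p) × m × f.

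The documents give none of p, m or f; the values below are assumptions. The 34 completers per arm come from Section 25.

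**Equal misreporting, true rates 10% control and 25% V2V (odds ratio 3.00):**

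| f | m | Control | V2V | Odds ratio |
|---|---|---|---|---|
| 10% | 10% | 10.9% | 25.75% | 2.83 |
| 30% | 20% | 15.4% | 29.5% | 2.30 |
| 50% | 30% | 23.5% | 36.25% | 1.85 |

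The risk difference is 15 × (1 − m × f) points, so it falls from 15.0 to between 14.85 and 12.75. False validated quitters among 34 controls number 34 × 0.90 × m × f = 0.3 to 4.6, which is 8% to 57% of that arm's validated quitters.

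**Unequal misreporting, no true effect (10% in both arms), m = 10% control and 30% V2V:**

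| f | Control | V2V | Difference | Odds ratio |
|---|---|---|---|---|
| 10% | 10.9% | 12.7% | 1.8 points | 1.19 |
| 30% | 12.7% | 18.1% | 5.4 points | 1.52 |
| 50% | 14.5% | 23.5% | 9.0 points | 1.81 |

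Swap the two misreporting rates and the odds ratios invert to 0.84, 0.66 and 0.55. At f = 0 the bias vanishes in this model.

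**Scale.** With 34 per arm and 10% in each, the 95% half-width for a difference is 1.96 × √(2 × 0.10 × 0.90 / 34) = 14.3 points before clustering. Every bias shown is smaller than that.

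**The case against.** The strongest reply is that abstinence is a secondary outcome of a pilot sized on retention, that Section 13 itself doubts pilot effect sizes, and that the bias under any of these assumptions is smaller than the sampling error. That stands, and it limits how much weight the point deserves. It does not remove the point, because sampling error shrinks in the next trial and this error would not.

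Four stronger readings are tempting, and the documents do not support them.

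- A reader might infer that students at zone 0 on entry pass validation whether or not they quit. They do not: Table 2 has saliva analysed only for those who report abstinence, so a student who reports vaping is never counted as abstinent. Nor does zone 0 at entry guarantee zone 0 at 6 months; a student who takes in more nicotine, or smokes, could read 1 or more.
- A reader might infer that the affected share cannot be seen. Sections 13 and 26 have baseline saliva taken for cotinine, and Section 13 has strip values entered by participant ID. If that applies at baseline, the zone is already recorded and only its use is missing. Table 2 also collects baseline e-cigarette frequency and amount.
- A reader might take the THC row of Table 2 as evidence that THC-only vapers will enrol. It is a separate row from e-cigarette use and shows only that the plan measures both.
- A reader might infer that the bias favours V2V. Students do follow a known school condition, so unequal over-reporting is possible, but nothing in the documents gives its size or direction. Equal misreporting pulls a true effect toward the null.

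**Conclusion.** The point holds in a limited form. Entry carries no nicotine or cotinine condition, the outcome is vaping abstinence, and the strip is its only biochemical check. For students who remain in zone 0 while vaping, a false claim of abstinence is therefore recorded as validated.

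The size is unknown because the affected share and the rate of false claims are not in the documents. The calculations show possible magnitude and direction under stated assumptions; they are not estimates for this trial. The feasibility outcome is untouched. This is an inexpensive improvement worth making, not a flaw that invalidates the pilot.

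**What to change.** Reconcile Sections 13 and 26 (saliva at baseline and 6 months) with Table 2 (6 months only) by reading the NicAlert strip for every participant at baseline and recording the zone. Then add to Section 13:

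- the number of students in baseline zone 0, by arm;
- validated abstinence overall and, as a pre-specified companion, among students with a baseline reading of 1 or more;
- a statement that abstinence in baseline zone-0 students is not biochemically verifiable.

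This has to be settled before enrolment. Section 13 has samples destroyed once values are entered and Section 12 gives banking as not applicable, so an unread baseline sample may not be recoverable.

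If baseline strips will not be read, use the past 7- and 30-day e-cigarette use already in Table 2 to describe low-exposure students by arm. A question on whether the product contains nicotine would be a poor substitute: Section 5 reports that most young users think vaping involves flavouring without nicotine.

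The cost is up to 80 strips, a few minutes per baseline visit and one analysis sentence. The companion estimate uses fewer students and is less precise. The marker is also imperfect: with a 90-day entry window a baseline 0 may mean only no recent use, and other tobacco can give a reading of 1 or more.

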how it worked/did not work; **iii)** their thoughts regarding our initial concepts; and **iv)** what they feel would help students use a mobile program. Interviews will employ a semi-structured open-ended approach, allowing for natural conversation with opportunities to explore unanticipated issues. Interviews will be recorded, transcribed, and coded.

The semi-structured interview is expected to last no more than 60 minutes. We will provide a \$100 gift card to the key informants for completion of this interview.

Compensation: Gift cards totaling up to \$120 (\$20-\$30 for each activity and the mini pilot) will be provided to adolescents for completion of Aim 1 activities. Gift cards of \$100 will also be provided to the key informants (school nurse and Vice Principal) and to the school nurses assisting with study activities (e.g., serving as the on-site point person for study recruitment, referring students requesting additional information regarding the study to research staff). There are two nurses at the high school, and we will provide a \$100 gift card per nurse.

See also Section #30, *Consent Process*.

Aim 2

We will recruit from 4-7 local high schools (that were not involved in Aim 1), selected for their high rates of racial/ethnic minorities and low SES status. Prior to recruitment, the study team will obtain IRB approval for the specific schools. To reduce the chances of imbalance across conditions, the schools will be matched based on percentage low income, percentage African American, and number of students, and divided into two sets of two. Within each set of two, we will randomly assign one school to each of the study conditions.

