Aim 2A (Feasibility) Hypothesis H1: *We will be able to recruit 80 adolescents (20/school, 40 per study condition), and $\geq 85\%$ will be retained in each study condition at 6-month follow-up.* We will estimate recruitment rates, overall and per condition. Also, for each condition, we will model 6-month retention, using generalized estimating equation (GEE) logistic regression to account for within-school clustering and dependence over time.

Proposed Sample Size. As appropriate for a pilot study, we are estimating our power and sample size based on the feasibility hypothesis (H1). Because pilot studies do not provide meaningful estimates of effect sizes due to the imprecision inherent in small samples, we base our proposed sample size of 40 students per condition (20 per school) on obtaining precision in estimating condition-specific retention rates, providing important information for design and recruitment for the future R01 study. Based on our prior study of adolescent smoking cessation, estimated intra-school correlation=0.01, for a design effect due to within-school clustering of $1 + [0.01 \times (20 - 1)] = 1.19$, and an effective sample size per condition of $40/1.19 = 34$. Based on our prior studies in

adolescents in school settings, we anticipate at least 85% retention. Thus, a conservatively wide 95% exact CI for per-condition retention rate is (68.9%, 95.0%).

Aim 2B (Monitor V2V Engagement and Assess Program Satisfaction) As the trial progresses, we will monitor engagement overall and by participant subgroups (e.g. by gender, race, age) as a formative assessment. Then, as the trial ends, we will also use this information as a component of our summative evaluation. We anticipate that engagement will lead to positive changes in acceptability, and satisfaction, and cessation.

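### The per-condition retention GEE has only two schools in each condition and no stated interval method; with a robust variance and z, a nominal 95% interval would cover about 61% on average

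*Combined protocol and SAP*

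**What the plan says.** Section 10 makes feasibility, including recruitment and retention, the primary outcome for Aim 2. For its analysis, Section 13 (Aim 2A) says: "for each condition, we will model 6-month retention, using generalized estimating equation (GEE) logistic regression to account for within-school clustering and dependence over time". It names no variance estimator, working correlation, reference distribution or small-sample method.

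The sample-size paragraph gives the reason for the study's size: "we base our proposed sample size of 40 students per condition (20 per school) on obtaining precision in estimating condition-specific retention rates". It takes an ICC of 0.01, a design effect of 1.19 and an effective sample of 34 per condition, and arrives at an exact 95% interval of 68.9% to 95.0% for retention. That is a planning figure. The text does not say whether the reported interval will be this one or will come from the GEE.

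On the number of schools, Section 11 (Aim 2) says the schools are "divided into two sets of two" and then "Within each set of two, we will randomly assign one school to each of the study conditions". Section 25 counts four Aim 2 schools with 20 students each. But Section 11 also says "We will recruit from 4-7 local high schools", and Section 6 has "80 adolescent e-cigarette users in 4-7 high schools".

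Table 2 lists "Retention: # of dropouts, reasons for dropping out" at the 6-month visit only.

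**The concern.** A robust (sandwich) variance estimates uncertainty from the spread between clusters. With one model per condition and two schools in it, that spread is a single difference between two school totals. If the schools happen to agree, the interval collapses; if they differ, it can be wide. A z multiplier makes no allowance for this.

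Precision of the per-condition retention rate is the plan's stated reason for its sample size and is meant to inform the later R01. An interval that is much too narrow would hand that study a retention figure with overstated certainty.

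Two text problems go with it. Retention is measured once, so there is no dependence over time to model. And the design effect depends on the number of schools, which the plan gives in two ways.

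**Working it through.** **Inputs.** From the plan: 20 students per school, 40 per condition, ICC 0.01, anticipated retention 85%. Two schools per condition follows from 40/20, from the pairing in Section 11 and from Section 25. Assumed here: robust variance with z on the logit scale, and ICC 0.05 as an alternative.

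**The plan's own figure.** Design effect 1 + 0.01 × 19 = 1.19; 40/1.19 = 33.6, rounded to 34. The Clopper-Pearson interval for 29/34 is 68.9% to 95.0%, width 26.1 points. It reproduces.

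**The robust interval with two equal schools.** Let p1 and p2 be the school proportions and p their mean. The intercept-only GEE with school as cluster has SE(p) = |p1 − p2|/(2√2). On the logit scale this is divided by p(1 − p). The same 34/40 retained (p = 0.85, logit 1.735, p(1 − p) = 0.1275) gives:

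| Retained per school | SE(p) | SE(logit) | 95% interval |
|---|---|---|---|
| 17 + 17 | 0 | 0 | zero width at 85% |
| 16 + 18 | 0.0354 | 0.277 | 76.7% to 90.7% |
| 15 + 19 | 0.0707 | 0.555 | 65.6% to 94.4% |

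A GEE fit in statsmodels with default settings reports the robust variance and returns the same interval for 16 + 18.

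**Coverage.** In the large-sample limit, coverage is (2/π) × arctan(1.96/√2) = 60.2%, whatever the ICC. For the actual sizes, all outcomes of two beta-binomial schools of 20 were enumerated exactly. A zero-width interval counts as covering only if it equals the truth. Trials with everyone retained count as misses (0.3% of trials at 85%).

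- True retention 80-90% in 0.1-point steps, avoiding values that a zero-width interval can hit: mean 60.9%, range 53.3% to 67.3%. With ICC 0.05 the mean is 61.3%.
- At exactly 85%: 71.8%, of which 4.9 points are zero-width intervals that equal the truth. At 85.01% it is 66.9%.
- At 85%, zero width occurs in 16.2% of trials, and the mean width is 13.8 points.
- With more schools per condition, at 85%: 79.4% for three (14/13/13) and 82.0% for four of 10.

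**Alternatives, two schools of 20.**

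- Exact interval on the effective sample, ICC 0.01: mean coverage 97.3%, minimum 96.0%, mean width 25.8 points at 85%.
- Model-based GEE interval with the ICC fixed at 0.01: mean 96.2%.
- Robust variance × K/(K − 1), where K = 2 is the number of schools, with t on 1 df: mean 83.2%, mean width 74.6 points. A small-sample correction does not rescue the robust interval.

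**The case against.** The plan never says it will use a robust variance with z. The only interval it names is the exact one, which performs well, and the retention hypothesis can be read as a point criterion (at least 85% retained). A reader might infer that the trial will report intervals covering 61%. The documents do not support that: they leave the choice open. What stands is that the named method, run with an ordinary default, gives the poor interval without any further decision by the analyst, and nothing links the exact interval to the analysis.

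Three other inferences go too far.

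- The 61% is an average over true retention of 80-90%. It is not the coverage at the anticipated 85%, which is 67-72%.
- The retention estimate and the 85% criterion are not put in doubt. With equal schools or an independence working correlation, the GEE estimate is the observed proportion. Only unequal schools with another working correlation could move it.
- Section 22's range of five to eight schools is not a further contradiction. It covers all aims, and one Aim 1 school plus four to seven Aim 2 schools gives that range.

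It can also be said that two schools per condition is not certain. That is so, but with three or four per condition coverage is still only about 80%, and 20 per school yields 80 students only with four schools (7 × 20 = 140).

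**Conclusion.** The point holds as an unspecified interval method with a serious consequence under a common default, and it should be fixed before analysis. If a robust variance with z is used on two schools of 20 per condition, nominal 95% intervals cover about 61% on average (53-67% across true retention of 80-90%, away from the special values), and mean width at 85% is about half the planned width. This rests on the plan's school size, ICC and two schools per condition, and on a variance choice that the plan neither makes nor rules out. The average barely changes at an ICC of 0.05. The point concerns the interval for retention only; the models for the cessation outcomes are a separate matter.

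**What to change.** Replace the retention GEE sentence in Section 13 with wording such as:

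> *Retention in each condition will be reported as the observed proportion with an exact (Clopper-Pearson) 95% interval on n/[1 + ICC × (mean school size − 1)], entering non-integer effective counts unrounded in the beta-quantile form, at ICC 0.01, with ICC 0.05 as a sensitivity analysis.*

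For 34/40 this gives 68.5% to 94.9% at ICC 0.01 (effective n 40/1.19 = 33.6) and 62.5% to 96.7% at ICC 0.05 (40/1.95 = 20.5). Alternatively, keep the GEE and state a model-based variance with the ICC fixed.

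Delete the mention of dependence over time. Reconcile the number of Aim 2 schools between Sections 6 and 11 (four to seven) and Sections 11 and 25 (two pairs, four schools), and update Section 22 to match. Then recompute the design effect for 40 students per condition: 1.19 with two schools, 1 + 0.01 × (40/3 − 1) = 1.12 with three, 1.09 with four.

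The cost is SAP wording only. The drawback is that the ICC is treated as known, and two schools cannot check it. If the true ICC is 0.05 but 0.01 is used, the exact interval's mean coverage falls to 91.9% (minimum 89.2%). Using 0.05 in that case gives a mean of 98.1%, hence the sensitivity analysis. At ICC 0.01 the interval is slightly conservative.
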